Intervention Content: The AMMA should be administered on day 1 of training, but it will be allowable to administer the AMMA within the first three training sessions. The NICT questionnaire should be administered between days 17 and 20 of training, but can be administered at the beginning of the post-test visit if it not completed during the intervention phase. The NICT questionnaire must be administered prior to the post-test assessments of CAP, cognition, or everyday function. If the NICT questionnaire is administered after the post-test assessments of CAP, cognition, or everyday function a protocol deviation will be noted. In this instance the NICT questionnaire will be coded as missing and will not be used in analyses. The post-training basic piano measure and music listening measure must be completed after all training content is delivered and prior to the post-test assessment visit. The trainer should confirm with the study coordinator that all scheduled intervention sessions have been completed and the basic piano or music listening assessments are completed prior to the post-test visit. The post-test visit can be rescheduled, if needed, but must occur within 18 weeks of baseline if no intervention was completed, or within 60 days of training completion date (≥ 16 sessions completed). Participant post-tests will be conducted after the intervention phase for those who complete between 1-15 sessions.

⁶ The sentence “Participant post-tests will be conducted after the intervention phase for those who complete between 1-15 sessions” and “(≥ 16 sessions completed)” was added for clarification.

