9.3 Sample Size

We expect up to 20% attrition after the initial in-person visit across the time period in which cognitive intervention study protocols will be administered. Our goal is to complete in-person screening visits for up to 450 participants in order to have up to 360 participants complete the study. We can tolerate higher rates of attrition. We require a minimum of 198 eligible participants with *at least* 99 individuals randomized to each condition (piano training, controls) to have adequate statistical power. With stratified randomization, this will result in *at least* 48 persons per MCI/no MCI subgroup.

Statistical power analysis using G*Power¹²³ in consideration of our pilot data effect sizes as well as attrition was conducted to estimate power. We will control type I error at .05 to achieve at least 80% statistical power.

To power **Specific Aim 1: To examine the efficacy of piano training to improve CAP, cognition, and everyday function among older adults**, a final n of 198 participants ($n=99$ per randomized condition) will achieve 95% power to detect a significant group x time interaction across baseline to immediate post-test, with an alpha of .05. This assumes a small effect size (f) of 0.10¹²⁴ (Cohen's f effect sizes are 0.10- small, 0.25- medium: f is roughly equivalent to $\frac{1}{2}$ of d when comparing two groups)¹²⁴.

To power **Specific Aim 2: To examine the moderating effects of MCI on intervention efficacy**, a final n of 168 will have .95 power at alpha .05 to detect medium effects ($f=.10$) for significant group x time x moderator three way interactions.

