9.5 Interim Data Analyses

Interim analyses will be conducted in June of 2019, after the pilot, first, and second replicates are completed. We expect that 140 participants will have completed post-test at this time. The purpose will be to confirm feasibility of the training conditions, to assess effect size on cognitive measures from pre- to post- training and adapt number of sessions, if warranted, and to monitor safety.

Interim analyses will be conducted to ensure the safety of the trial. Per NIA, this project does not meet the criteria for requiring a formal Data and Safety Monitoring Plan or Data Safety Monitoring Board because it is not a Phase III clinical trial as defined by NIH. As a behavioral intervention study, this is a phase II efficacy trial¹. At interim analysis, [name] will compare the number of adverse events between the two randomized conditions to assess safety. The two groups will also be compared on attrition rates. Any significant differences between the two conditions in adverse events or attrition rates will be further investigated by [name]. If there is a significant imbalance, confirmed, then [name] will report the findings to the Clinical Trial Coordinator, [name], who is unblinded. The Clinical Trial Coordinator will work with the IRB to decide if the study should be terminated early.

Interim analyses will be conducted to ensure the feasibility of study intervention adherence. If at interim analyses, less than 75% of participants randomized to an arm complete at least 16 sessions (80% of prescribed 20), the intervention arm will be deemed not feasible. If this occurred for both arms, the study will end.

Finally, interim analyses will examine the potential efficacy of the piano training arm. Effect sizes and confidence intervals for all cognitive outcomes will be calculated for pre- to post- training relative to controls. We expect that the piano training arm will produce an improvement of at least $d=0.25$ from baseline to post-test on at least one of the cognitive measures of verbal fluency (phonemic, category or switching), Trails A or B, or Digit Coding, relative to active controls. If an effect size from pre- to post- training relative to controls of this

magnitude is not observed on at least one of these outcomes, we will adapt study procedures by changing the number of training sessions from 20 to 25. In this instance number of training sessions completed will be examined as a covariate in final analyses.

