9.6 Final Data Analyses

Dealing with Score Distribution. We will inspect the distribution of scores to confirm that parametric statistical testing is appropriate. In the event that distributional properties do not support parametric tests, we will compare the results from conventional parametric analyses with (a) results from similar nonparametric testing (e.g., Wilcoxon signed ranks test), (b) results from parametric analyses conducted after the non-normally distributed variables are transformed to improve normality to compare the results with the conventional parametric analyses, and (c) Any illegal values or outliers of $\geq \pm 3z$ will be checked for accuracy with the raw data.

Composite Outcomes. Data reduction in the form of principal component factor analysis (PCA) will be used to derive composite outcomes of CAP, cognition, and everyday function for analyses to reduce the number of comparisons. Baseline data across CAP, cognitive, and everyday function outcomes will be factor analyzed using pairwise deletions. Based on the number of factors derived and factor loadings of the individual measures (.4 or greater), outcome composite scores will be calculated after transforming the baseline data to z scores while taking into account the directional scaling of the items. Post-test scores will be standardized based upon the baseline mean and SD. The baseline factors and loadings will be applied to calculate post-test composite scores.

Preliminary/Descriptive Analyses. Prior to the analyses described below, we will conduct one-way ANOVA or Chi-square analyses as appropriate comparing the randomized groups at baseline on age, race, education, sex, MoCA, GDS, hearing and vision, to ensure that the study randomization procedures were successful. We will also confirm the equivalence of the two randomized conditions by comparing the NICT questionnaire responses. The total across the six items relevant to cognition will be calculated and examined in analyses. If even a marginally significant ($p < .1$) difference is observed for any of these study variables, the pertinent variables will be included as covariates in subsequent analyses.

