Specific Aim 1: To examine the efficacy of piano training to improve CAP, cognition, and everyday function among older adults. We will compare changes in performance for piano training relative to control across the two measurement points (baseline, immediate post-test). We will use the PCA-derived composites of CAP and cognition, and everyday functioning as outcomes. We will use repeated measures analyses of variance within the mixed effects models, examining group as the between-subjects factor and time as the within-subjects factor. The group x time interaction will indicate whether the participants randomized to piano training change at differential rates over time relative to those randomized to the control group. This output will be obtained for each of the composite outcomes (CAP, cognition, and functional abilities). For aim 1 analyses and the composite outcomes of CAP, cognition, and everyday function, we will apply Holm-Bonferroni adjustments¹²⁵ to reduce Type I error. Specifically, the Holm-Bonferroni procedure uses a step-down process whereby p-values are sorted from lowest to highest, then the lowest p-value is used in its raw version, the second lowest p-value is multiplied by two, the third lowest p-value is multiplied by three and so on until the adjusted

p-value reaches or exceeds the pre-specified threshold for statistical significance, in our case a two-tailed p value of .05.

Intent-To-Treat Approach. We expect that some participants will not complete their intended followup according to the protocol for a variety of reasons, generating missing values. Intent-to-treat (ITT) analysis has become a widely accepted method for dealing with this issue. To maximize available information, we will employ statistical techniques that allow for the inclusion of missing data. Specifically, we will use linear mixed effects models to analyze data. This advanced analytical method allows for the inclusion of participants with missing data, so long as data are missing at random and offers flexibility with regard to the specification of the variance/covariance structure, which often leads to improved fit of the analytical model to the actual data. If there is non-ignorable missing data, we will apply pattern-mixture mixed effects models to assess the sensitivity of our findings with regard to missing data¹²⁶.

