The randomized groups did not differ in sex, $\chi^2(1)=.787, p=.375$, ethnicity $\chi^2(1)=.167, p=.683$, or race, $\chi^2(1)=.045, p=.832$. The Music Reading Assessment scores did not differ between the two groups, $t(266)=-.958, p=.338$. The randomized groups did not significantly differ in age, $F(1,266)=.293, p=.589$, education, $F(1,266)=.369, p=.544$, MoCA, $F(1,266)=.427, p=.514$, or GDS, $F(1,266)=.943, p=.332$. However, there were marginally significant group differences for PTA in the left ear, $F(1,266)=3.31, p=.070$ and statistically significant group differences for both PTA in the right ear, $F(1,266)=6.69, p=.010$, and visual acuity, $F(1,266)=8.99, p=.003$. The music listening group tended to have worse hearing, while the piano training group tended to have worse visual acuity. See Table 1. The groups also differed significantly in their expectations regarding potential benefits of their randomized group, $F(1,214)=15.07, p<.001$. The piano training group had an average rating of 5.55 while the music listening group had an average rating of 4.99, indicating the piano training condition had higher expectations about the potential effects of their randomized condition. The piano training group also rated their condition as more challenging with 92% agreeing that the intervention was challenging as compared to 86.3% of the music listening group indicating their condition was challenging ($p<.001$).

Principal component analysis with varimax rotation was conducted to reduce the number of variables for analyses. Please see Supplemental Table A for details. The first factor reflected cognitive performance speed and included the Trail Making Test, Digit Coding, and the TEA visual elevator and phone search subtests. The second factor included all three verbal fluency subtests. The third factor reflected CAP and included DDT, DSI, TCS, and WIN. The fourth factor included two indices from the TEA phone search while counting and visual elevator accuracy. The fifth composite included ATTR across- and within- channel performance. Baseline composites of cognitive performance, verbal fluency, ATTR, CAP, and everyday function were created by averaging z scores after the reverse-scaling of items with negative factor loadings. Post-test scores were standardized

by baseline means and *SDs*. Timed IADL performance did not significantly load on any factor and was thus examined separately.

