In the primary analyses, we examined whether performance changed differentially by random assignment across composite outcomes from baseline to post-test as indicated by a significant group-by-time interaction. Covariates included hearing PTA, visual acuity, and expectations. The group-by-time interactions were not statistically significant for any of the outcomes ($ps > .194$). See Table 2. The results did not change when we included only those who were adherent ($ps > .180$). See Supplementary Table B. Piano training did not significantly enhance CAP, cognition, or everyday function as compared to music listening. We further examined if intervention effects varied by MCI status (Supplementary Table B). There were no significant group-by-time-by-MCI status interactions indicating those with and without MCI did not show differential benefit ($ps > .245$). Thus, MCI did not significantly moderate the effects of piano training.

Effect sizes for piano training as compared to music listening are shown in Table 3. Improvements were not evident in the primary analyses, adherent analyses, or the subsample without MCI on measures of CAP, cognition, or everyday function. Participants with MCI randomized to piano training showed potential small effect sizes for improvement relative to music listening on Trails A, Digit Symbol Coding, and one subtest of the TEA ($ds \geq 0.25$). Raincloud plots of individual assessment and composite variables are included in the supplemental materials.

Results indicated significant effects of time for ATTR in all models and significant effects of time for CAP in the primary and adherent analyses indicating improved performance from pre- to post- training. Significant effects of time were found for cognition and TEA in the primary and adherent analyses, indicating a tendency for decline across time. With respect to covariate effects, CAP, ATTR, and cognitive performance were significantly impacted by hearing. Similarly, Timed IADL and cognitive performance varied significantly by visual acuity. Those with poorer hearing or vision tended to perform worse on these outcomes. Interestingly,

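### The Aim 1 group x time test is valid but does not use the equal expected baselines given by randomisation; a common-baseline model with pre-randomisation covariates only would be somewhat more precise at almost no cost

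*Combined protocol and SAP*

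**What the plan says.** Section 9.6 (Specific Aim 1) compares change across baseline and immediate post-test for each composite, "examining group as the between-subjects factor and time as the within-subjects factor". The group x time interaction is the test. No constraint is placed on the baseline means, and Table 14.2 reports a separate Group term for every composite. Section 5.5 randomises 1:1, stratified by MCI status.

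The preliminary-analyses paragraph of Section 9.6 compares the arms on baseline characteristics and adds: "We will also confirm the equivalence of the two randomized conditions by comparing the NICT questionnaire responses". If any of these variables differs at p < .1, "the pertinent variables will be included as covariates in subsequent analyses". The expectations questionnaire is not a baseline measure. Section 6.1 states: "The NICT questionnaire should be administered between days 17 and 20 of training". Section 14 reports: "The piano training group had an average rating of 5.55 while the music listening group had an average rating of 4.99". It then confirms the model: "Covariates included hearing PTA, visual acuity, and expectations".

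Section 9.5 has a second covariate of this kind, used only if the programme is lengthened to 25 sessions: "In this instance number of training sessions completed will be examined as a covariate in final analyses".

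Section 9.3 claims that 198 participants "will achieve 95% power to detect a significant group x time interaction across baseline to immediate post-test", with f = 0.10. It gives no correlation between baseline and post-test.

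**The concern.** With two visits and a free baseline mean in each arm, the group x time coefficient is the difference in mean change. It subtracts the whole observed baseline difference, although under randomisation that difference is chance. A model with one common baseline mean, or post-test adjusted for baseline, subtracts only the part that predicts the post-test score. It is never less precise in large samples, and it equals the change-score contrast only when the baseline SD is r times the post-test SD.

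What is at stake is precision on the primary comparison, obtainable from data already collected. The covariate rule is tied to this. Given a post-randomisation score that differs by arm, baseline means are no longer equal in expectation, so a common-baseline model containing that score would be biased. Changing the model without changing the rule would replace a valid test with a biased one.

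**Working it through.** **1. The plan's own figure.** Inputs from Section 9.3 are N = 198, f = 0.10 and alpha .05. For the G*Power within-between interaction, lambda = f² x N x 2/(1 - r).
- At r = .70, lambda = 0.01 x 198 x 2/0.30 = 13.2 and power is .951, which matches the stated 95%.
- At r = .50, power is only .80. So r = .70 is implied but not stated.
- Under this reading f = 0.10 is a 0.40 SD difference in change.
- Section 9.3 also says that f is roughly half of d, which gives 0.20 SD. With Var = 4(1 - r)/n and n = 99 per arm, 95% power then needs r = .925.

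**2. Variance saving.** Let k = post-test SD/baseline SD, p = share with a post-test (missing at random), n = completers per arm and baseline SD = 1.
- Planned contrast: 2[k²(1 - r²) + p(1 - kr)²]/n.
- Common baseline: 2k²(1 - r²)/n.
- Saving = p(1 - kr)²/[k²(1 - r²) + p(1 - kr)²].

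At r = .70, k = 1 and p = .80 (Section 9.3 expects up to 20% attrition), the saving is 0.8 x 0.09/(0.51 + 0.072) = 0.072/0.582 = 12.4%.

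| r | Saving | 198 completers are worth |
|---|---|---|
| .50 | 21.1% | 251 |
| .70 | 12.4% | 226 |
| .83 | 6.9% | 213 |
| .925 | 3.0% | 204 |

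At the realised 76% retention, the r = .70 figure is 11.8%.

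**3. Sensitivity to assumptions.**
- Unequal SDs at r = .70: 21.0% for k = 0.9, 6.4% for k = 1.1 and 2.7% for k = 1.2. At r = .92 and k = 1.1 the saving is 0.1%.
- Class variance, illustrated with an assumed intraclass correlation of .05 and 8 per class, adds 7 x .05 = 0.35 to both variances. Then 12.4% becomes 0.072/0.932 = 7.7%, and 3.0% becomes 0.9%.
- For cognition, the ratio of the Group to the group x time standard error in Table 14.2 is 1.84/0.84. Treating the data as complete pairs, it implies r of about .82 if time was coded 1/2, or .90 if coded 0/1. The savings at 80% retention are then about 7% or 4%.

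**4. Power** with 99 completers per arm and p = .80: from 95.6% to 97.5% (0.40 SD, r = .70), or from 95.2% to 95.8% (0.20 SD, r = .925).

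**5. Expectations in a common-baseline model.** The arm gap is 5.55 - 4.99 = 0.56, and the cognition coefficient in Table 14.2 is -1.96. Adjusting for expectations creates an apparent baseline difference of about 1.96 x 0.56 = 1.10 points. The constraint passes on about (1 - r) of it: 0.33 at r = .70, 0.19 at .83 and 0.09 at .92. Simulation with no true effect (2,500 trials per setting, 99 pairs per arm, assumed composite SD 10 and expectations SD 1) gave 0.32, 0.18 and 0.08. The planned contrast with expectations included averaged -0.03 to 0.01, so it is not biased this way in complete pairs.

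**6. Reported trial, approximate.** From Table 14.2, adjusted estimate = group x time + (1 - r) x baseline difference, with SE multiplied by sqrt((1 + r)/2). The baseline difference is Group (time coded 0/1) or Group + group x time (coded 1/2). Those terms are already adjusted for expectations, so undoing that adds coefficient x 0.56, with a sign that depends on the arm coding.
- At r of .70 or more, the largest |t| over all composites and codings is about 1.2 (verbal fluency).
- At r = .50, cognition coded piano minus music, time 0/1: 0.39 + 0.5 x (-2.62 - 1.10) = -1.47. SE = 0.84 x sqrt(0.75) = 0.727, so t = -2.02, against piano. Under the opposite arm coding, no composite exceeds 1.35.

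**The case against.** The strongest reply is that the plan is coherent as it stands. The aim is worded as change, the power calculation is for the group x time term, Aim 2 extends it to a three-way interaction, and Table 14.3 reports pre-to-post effect sizes. The planned test is unbiased with respect to baseline, the power gain is one or two points at most, and the trial is complete. All of that stands, and it makes this an efficiency point. It does not remove the gain. The mediation analysis in Section 9.6 already adjusts the post-test score for the pre-test score, so the approach is not foreign to the plan.

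It can also be said that the bias in step 5 arises only in the proposed model. That is correct, and it is why the two changes must be made together.

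Three stronger readings are not supported:
- A reader might take 12% as the expected gain. It rests on one of two readings of f and on equal SDs. Section 9.6 scales post-test scores by the baseline SD, which does not make the SDs equal.
- A reader might infer that the reported null would survive the change at every r. Step 6 supports this at r of .70 or more, but not for cognition at r = .50 under one arm coding.
- The degrees of freedom in Section 14 (214 for expectations, 266 for baseline variables) imply scores for 216 of 268 people. A reader might infer that 52 are lost to the primary contrast. But Table 14.3 has 198 in the overall analysis, so about 268 - 198 = 70 lack an analysed post-test, and Section 6.1 lets the questionnaire be given at the post-test visit. Most of the 52 probably had no post-test and would add little to a change contrast.

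**Conclusion.** The point holds as one of efficiency. The Aim 1 test is valid in how it handles baseline, but it does not use the baseline equality that randomisation provides. The saving is about 3% to 21% of variance for r from .925 down to .50, given equal SDs, 80% retention, data missing at random and independent participants. For cognition, the primary outcome, the lower part of that range is likelier. The true r and the SD ratio are not in the documents, the gain can be close to zero if the post-test SD is larger, and class-level variance would reduce it.

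The gain is safe only if covariates are limited to pre-randomisation values. The expectations score fails that condition, and so would sessions completed. The figures of 0.1 to 0.3 points assume a composite SD of 10 and no true effect. None of this shows that the reported group x time estimates are biased by the expectations covariate in complete pairs, and the approximate check shows no significant benefit of piano training.

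**What to change.** In Section 9.6, Aim 1, specify for each composite a two-time-point mixed model on all randomised participants. It should have a common baseline mean, time, group at post-test, MCI stratum as randomised (not as later adjudicated), MCI x time and an unstructured covariance. Make the adjusted post-test difference the primary estimate. Limit covariates to values measured before randomisation, such as baseline hearing and vision.

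Amend the covariate rule in Section 9.6 so that the expectations score does not enter this model. Amend Section 9.5 so that sessions completed does not either, should the number of sessions be increased. Both can be examined in separate exploratory analyses.

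Report two sensitivity analyses: the unconstrained group x time result, and a run excluding baseline measures given after randomisation, which Section 6.1 permits. Label any re-analysis of the completed trial as post hoc.

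The cost is a small change to SAP wording and model code plus two extra runs, with no new data. The downside is that the constraint relies on baselines unaffected by allocation, so late baseline assessments must be flagged in the data.
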